## External Validity and Gestational Age

We will weight observations in our analysis sample by the inverse of the ratio of the number of users of their gestational age in our sample and the number of users of their gestational age in the population of MomConnect users who are above 18. Due to our enrolment schedule, our sample will overrepresent pregnant women who register for MomConnect at a later gestational age than is the case for the overall population of women on MomConnect. Since these women may be different on unobserved characteristics correlated with treatment effectiveness and women registering later will be exposed to MomConnect for a shorter time, post-stratification weights will potentially improve the external validity of the estimates when extrapolating results beyond the specific sample to the population of all MomConnect users.

## Subgroup analysis

We will also do some exploratory subgroup analysis based on the following characteristics:

1. **Age:** We might expect mothers who are above 35 (advanced maternal pregnancy) to act differently than mothers who are below 35 given the higher risks associated with pregnancies for mothers above 35.
2. **The number of children the mom has:** We might expect first-time mothers to rely more on MomConnect than incumbent mothers who could pull from previous experience.
3. **Education level:** Since education levels are associated with socioeconomic status, we might expect mothers with less formal education to have less access to knowledge and resources on how to adopt healthy behaviors
4. **Income quartile:** We might expect mothers from poorer households to have less access to knowledge and resources on how to adopt healthy behaviors.
5. **Province:** The health service infrastructure differs strongly across South African provinces. We will explore in which provinces MomConnect is particularly effective.
6. **Weeks pregnant at sign-up:** The earlier in their pregnancy mothers sign-up with MomConnect, the longer they are exposed to messaging. We would therefore expect mothers signing up earlier to see larger benefits. We will use the stratification bins for weeks pregnant for this analysis.

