### INTERVENTION

The randomized control trial will consist of one control arm, resembling the status quo MomConnect messaging model, and three new treatment arms. The study will evaluate the relative effect of three new behaviorally-informed program models on key health outcomes. The table below summarizes the different models (treatment arms) proposed in this study:

*Table 1: Treatment Arms*

Name	Form	Description
ARM	WhatsApp	The appointment reminder model (ARM) is the current MomConnect WhatsApp model (control). Mothers receive weekly conversation starter messages reminding them about their upcoming clinic appointments, providing more comprehensive and relevant maternal health information only after mothers respond to the appointment reminder.
RCM	WhatsApp	In the relevant content model (RCM), Mothers receive weekly conversation starter messages, which carry both clinic appointment reminders along with some maternal and infant health information relevant to their pregnancy/postpartum stage. In addition, a list of “frequently asked questions” (FAQs) relevant to the week of pregnancy the mother is in are provided so that mothers can engage further with maternal health information topics relevant to them.
	SMS	Mothers receive twice weekly conversation starter messages of 160 characters each, which carry both clinic appointment reminders as well as maternal and infant health information , relevant to their stage of pregnancy or the age of their baby. Mothers can access the list of frequently asked questions relevant to their week of pregnancy via USSD.
RCM + BCM	WhatsApp	In addition to the RCM, this arm also includes the browsable content model (BCM). The BCM adds an option to browse a menu of relevant maternal and infant health information that mothers can explore themselves over WhatsApp. All in all, the RCM+BCM arm includes appointment reminders, clinical information, a browsable menu, and prompts to relevant stage-based topics. Mothers also receive weekly conversation starter messages as in all other models.

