### RESEARCH QUESTIONS

The table below highlights the key research questions that the study aims to answer.

Table 2: Research Questions

Category	Research Question	Decision Relevance
Primary Research Questions		
Health Outcomes	Which version of MomConnect improves key maternal and infant health outcomes?	Expansion of the most impactful MomConnect treatment arm across South Africa
Secondary Research Questions		
Message Delivery	Are maternal and infant health outcomes better if MomConnect is administered over SMS as compared to WhatsApp for the RCM model?	Decision on standardizing the RCM model in SMS or WhatsApp format
Directed Attention	Which aspects of the content models do women engage with the most?	Improved MomConnect message format
Perceived reliability	Which health-related topics do pregnant women find most reliable/trustworthy?	Improved MomConnect message content
Socio-economic characteristics	Which socio-economic characteristics are correlated with higher/lower effectiveness of MomConnect?	Adjusting content for groups for which MomConnect is less effective

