## RECRUITMENT & RANDOMIZATION PROCEDURE

Pregnant women presenting at public health facilities across South Africa are asked by nurses, in accordance with national health guidelines, if they would like to join the MomConnect platform. This process has successfully registered 60% of pregnant women across the country (Benjamin et al. 2018). The recruitment process for this study will follow the same procedure and is unchanged by the study.

Women will register for MomConnect at a health facility by filling out a USSD recruitment survey. The survey asks specific questions about each pregnant woman. From the recruitment survey, we will learn the gestational age of pregnant women, how old they are, and which province they are from. Mothers will then be asked if they would like to take part in a research study to improve the MomConnect service and will be sent a consent message via WhatsApp. Consenting participants will then be assigned to different strata (one of three categories for gestational age: 16-20 weeks, 21-25 weeks, 26-30 weeks; one of two categories for age: 30 and under, over 31; and one of nine categories for province). Next, they will be sorted into one of 54 strata according to their unique combination of weeks pregnant, age, and province. Because recruitment is occurring on a rolling basis, we use sequential randomization within strata to improve balance within strata, across study arms. Participants will then be assigned one of the four messaging arms according to an ex-ante random schedule within each stratum. In this way, there will be a similar way of women assigned to each of the four arms within each stratum.

After consent and randomization participants will be invited to a (non-mandatory) baseline survey via WhatsApp (or USSD for the RCM-SMS arm) and will start to receive content based on which of the four study arm message models they were randomly assigned to. Women who do not give consent to be part of the study will receive the status-quo WhatsApp MomConnect service (equivalent to the Control arm) and be excluded from the study.

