### Primary Specification

For our primary research question, we will estimate the following regression specification in order to understand the impact of each treatment arm on the four primary outcomes (immunizations, ANC visits, knowledge/attitudes index, behavior index):

$$Y_{is} = \alpha + \sum_j \beta_j T_{jis} + \delta_s + \epsilon_{is}$$

- $Y_{is}$  is the midline or endline primary outcome of mother  $i$  in stratum  $s$
- $T_{jis}$  is the treatment indicator for mom  $i$  and treatment arm  $j$  in stratum  $s$ .  $\beta_j$  is the impact of treatment arm  $j$  relative to the status quo model (control).
- $\delta_s$  is a vector of dummies corresponding with each stratum (province by age-range category by weeks pregnant category at time of recruitment)
- $\epsilon_{is}$  is the individual level error term. We will estimate heteroskedasticity-robust standard errors using the Huber-White sandwich estimator.

In primary analysis, we will use the separate specification to test the differences in outcomes between the WhatsApp ARM control arm and each of the two other WhatsApp treatment arms (RCM, and RCM + BCM) as well as the difference between RCM and RCM+BCM and the difference between RCM and RCM-SMS.

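### Every arm receives MomConnect, so subgroup results can show who gains more from a new model over ARM, not for whom or where MomConnect itself is effective

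*Combined protocol and SAP*

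**What the plan says.** The Intervention section sets the comparison: "The randomized control trial will consist of one control arm, resembling the status quo MomConnect messaging model, and three new treatment arms". Table 1 adds that "The appointment reminder model (ARM) is the current MomConnect WhatsApp model (control". Under Recruitment & Randomization Procedure, "Women who do not give consent to be part of the study will receive the status-quo WhatsApp MomConnect service" and are left out of the study, so they provide no untreated group either. The Primary Specification defines each treatment coefficient "relative to the status quo model (control"), and the Empirical Specification places its intent-to-treat effect against the same arm.

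Two places ask for something else. The fifth research question in Table 2 is "Which socio-economic characteristics are correlated with higher/lower effectiveness of MomConnect", and the decision it serves is "Adjusting content for groups for which MomConnect is less effective". The province item under Subgroup analysis reads "We will explore in which provinces MomConnect is particularly effective". The subgroup analysis is labelled exploratory. The section lists six characteristics and gives no model or test for differences between subgroups.

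**The concern.** Asking where a programme is effective requires a comparison with its absence. Here nobody is without it: the trial compares versions of MomConnect. A subgroup estimate from the planned regression is the outcome under a new model minus the outcome under ARM. It can be small because the new model does little for that group, or because ARM already does a good deal for it. The trial cannot separate these two explanations.

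This matters because Table 2 attaches a decision to the answer. If a small gain over ARM is reported as MomConnect being less effective in a group, content could be revised for a group that the programme already serves well, while a group that it serves less well is passed over.

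**Working it through.** **1. What the design figure measures.** Inputs from Sample Size (Table 4): control rate 0.68, difference 5 points, alpha 0.05 (taken as two-sided), power 0.80. With the mean rate (0.68 + 0.73)/2 = 0.705:

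n per arm = [1.960 × √(2 × 0.705 × 0.295) + 0.842 × √(0.68 × 0.32 + 0.73 × 0.27)]² / 0.05² ≈ 1305.

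Unpooled variance gives 1302, and power at 1300 per arm is 79.9%. The plan's 1300 is reproduced, as is enrolment: 5200/0.60 = 8667. The 68% is the rate assumed for the control group, that is, under status-quo MomConnect, and the 5 points are a difference between versions. No rate without MomConnect is assumed or measured anywhere.

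**2. What a subgroup estimate identifies.** For group g, let u be the rate with no programme, a the rate under ARM and t the rate under a new model. The trial observes a and t only.

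- Gain over ARM: G = t − a (identified).
- Total effect of the new model: E = t − u = G + (a − u) (not identified, because u is not observed).
- Difference between groups A and B: E_A − E_B = (G_A − G_B) + [(a_A − u_A) − (a_B − u_B)].

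The bracket is the difference between groups in what ARM itself achieves. Ranking groups by G matches ranking them by E only if the bracket does not outweigh the first term. No trial data bear on the bracket.

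**3. Illustration with assumed rates.** None of these rates comes from the documents.

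| Group | No programme | ARM | New model | Gain over ARM | Total effect |
|---|---|---|---|---|---|
| A | 0.50 | 0.72 | 0.74 | +2 points | +24 points |
| B | 0.64 | 0.66 | 0.73 | +7 points | +9 points |

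The trial would see +2 and +7 and place A lower; the total effects have the opposite order. Now vary only A's no-programme rate:

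| A, no programme | A, total effect | B, total effect | Order reversed? |
|---|---|---|---|
| 0.50 | +24 | +9 | yes |
| 0.60 | +14 | +9 | yes |
| 0.67 | +7 | +9 | no |
| 0.70 | +4 | +9 | no |
| 0.72 | +2 | +9 | no |

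The order flips when 0.74 − u_A > 0.09, that is, when u_A < 0.65. The observed data are the same in every row, so the trial cannot tell which row applies.

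**4. How far the wording problem extends.** The fifth research question, its decision and the province item name the effectiveness of MomConnect directly. The age, education and income items concern how women behave or what knowledge and resources they have, and claim nothing about a total effect. The items on number of children and weeks pregnant at sign-up refer to reliance on MomConnect and length of exposure to messaging. These also apply to control women, but either could plausibly modify a gain over ARM, so those two items are ambiguous rather than wrong.

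**5. Estimator.** The Primary Specification contains arm indicators and stratum dummies only. Without interaction terms it gives no direct estimate of how an arm's effect differs between subgroups.

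**The case against.** The strongest reply is that MomConnect, in the disputed sentences, is shorthand for the versions under test. Background & Motivation and Intervention both describe the aim as the relative effect of three new models, Sample Size speaks of comparing versions, and the regression is defined against ARM. Subgroup analysis proposes no other comparator, so no wrong number would be produced. A large ARM effect is also not the natural assumption, since Background & Motivation describes the current push messages as generic reminders that may leave many mothers under-engaged. The illustration needs ARM to add 22 points in group A (0.72 − 0.50) and 2 in group B (0.66 − 0.64), and nothing in the plan supports either value. Finally, reviewing new content where it adds little over reminders is a reasonable use of the incremental effect.

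Much of this stands. The estimates would be correct as gains over ARM, and a content decision can sensibly rest on them if it is described that way. The shorthand reading does not fully settle the matter, however. The primary question in the same table asks which version of MomConnect improves outcomes, so the plan makes the distinction when it wants to. The fifth question drops it and attaches a decision to the broader quantity, and no section says that subgroup results are gains over ARM or lists this as a limitation.

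A reader might infer more: that the content decision will go backwards, that the whole subgroup section is misconceived, or that the main analysis is compromised. The documents support none of these. Reversal depends on no-programme rates that nobody measures; only the research question with its decision and the province item clearly carry the wording; and the primary contrasts do not depend on it. The missing interaction model, taken alone, would be no more than missing detail in an exploratory analysis.

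**Conclusion.** The point holds as one of identification and interpretation. That every estimable subgroup effect is relative to ARM, or between new models, follows from the plan's own description of its arms and its regression, and needs no outside figure. The fifth research question, its decision and the province item name a quantity that the design cannot estimate.

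The size of any resulting error is unknown. Mislabelling a group is possible where ARM already delivers much of the benefit. The reversal shown (gains of +2 and +7 points against total effects of +24 and +9) rests wholly on assumed rates and disappears once group A's assumed no-programme rate reaches 0.65, with the other rates held fixed. The subgroup analysis is exploratory, and the primary analysis, its multiplicity adjustment and the sample size stand as they are. The correction is still worth making, because it changes what the trial may conclude on a stated research question and costs very little.

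**What to change.** 1. Reword the fifth research question in Table 2 and the province item under Subgroup analysis to: differences by subgroup in the effect of RCM, RCM+BCM and RCM-SMS relative to ARM, and of RCM-SMS relative to RCM. The last contrast matches one already planned in the Primary Specification.
2. Restate the decision as concerning groups that gain less from the new models over ARM.
3. State, in Subgroup analysis or under Limitations, that the overall effect of MomConnect by subgroup is not identified because all arms receive it.
4. Estimate the differences by adding arm-by-subgroup interaction terms to the Primary Specification model, with a joint test per characteristic, reported as exploratory. Include the subgroup's own main effect where the stratum dummies do not absorb it: number of children, education, income, and age split at 35, since the strata split age at about 30.

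The cost is a few sentences and some terms in an existing model, plus the loss of the broader claim about where MomConnect works, which the design could not support. Data collection, randomisation, primary analysis and sample size do not change.

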## LIMITATIONS AND CORRECTIONS TO DATA

### Attrition

#### Attrition due to opt outs

There is a possibility that mothers opt out of receiving MomConnect messages. Under South Africa's Protection of Personal Information (POPI) Act, if users want to opt out of messaging, they can choose to delete their information from MomConnect, including their contact information. This is a threat to internal validity if the mothers who drop out are different from the mothers who continue to receive messages in ways correlated to knowledge and adoption of healthy behaviors.

Based on previous data from on opt out rates for the status quo of MomConnect, this is a very low proportion of mothers. However, in order to further reduce the risk of attrition bias, Reach has introduced a question in the user flow for mothers to specify what they are opting out of. If they are opting out of messages, they can therefore still be contacted for our surveys.

## Attrition due to non-response

There is a high likelihood that some mothers will choose not to respond to some or all questions in the surveys. We expect a response rate of at least 60% for phone surveys. Bias can occur if the mothers who don't respond to surveys differ meaningfully from those who do respond across treatment arms. In order to maximize response rates, we will incentivize survey responses by offering airtime credits. We will also utilize different callback protocols during our endline phone survey to maximize response rates and make up to 7 attempts for each study participant.

### Checks for attrition

We will check for differential attrition to see if mothers who respond are different across messaging arms. In order to do this, we will regress a binary variable representing response on treatment status and use the same controls as defined in the main specification. We will also check if mothers who respond to our endline survey differ across baseline variables across treatment arms. We will also check for selective attrition to see if baseline characteristics differ across responders and non-responders in general. This will be informative about the generalizability of our results with respect to the whole user base of MomConnect. We will also apply bounds assuming worst and best-case scenarios following Horowitz and Manski (2000) to bound treatment effect estimates.

### Missing Values

Amongst mothers who do respond to our survey, some might respond “don’t know” or “refuse.” For knowledge based questions, we will treat “don’t know” responses and refusals as incorrect answers as it is a fair assumption that mothers who skip responding to a quiz question are choosing to skip because they do not know the correct answer. For behavioral questions, we will treat “don’t know” responses and refusals as missing given the likelihood that the mom might legitimately not recall doing a particular behavior.

### Multiple Hypotheses Adjustments

The most relevant decision from this study to inform scale-up of the program will be informed by which WhatsApp treatment arm is best for key primary health outcomes. We will test the following 8 null hypotheses:

- The difference in  $outcome_i$  between ARM and RCM is zero
- The difference in  $outcome_i$  between ARM and RCM + BCM is zero
- The difference in  $outcome_i$  between RCM and RCM + BCM is zero
- The difference in  $outcome_i$  between RCM and RCM + SMS is zero

where the subscript  $i$  captures the two main outcomes, immunizations and ANC visits.

Given that there are multiple hypotheses to test, standard statistical significance levels ( $\alpha = 0.05$ ) would likely result in finding significant outcomes by chance alone. Indeed, the probability of finding at least one false significant result (rejecting the null when it is true), would be  $1 - (1 - 0.05)^8 = \sim 34\%$ .

[figure not shown]
To correct for this, we will adjust for multiple hypotheses by applying a false discovery rate adjustment (FDR) following Benjamini et al. (2006). In particular, we will use the sharpened q-values discussed in Anderson (2008). This correction will control for the expected proportion of Type 1 errors. In our analysis, we report both corrected and uncorrected p-values.

These multiple hypothesis adjustments will focus on analysis of the four treatment arms and two primary outcomes specified given that these hypotheses affect potential scale-up decisions. Secondary outcomes will be exploratory.

## APPENDIX

### Appendix A: MomConnect Logic Model

Figure 1: MomConnect Logic Model

